**Inclusion/Exclusion Criteria:**

**Inclusion Criteria:**

1. Age  $\geq 18$ .
2. Active duty or DoD beneficiary
3. Diagnosed with rheumatoid arthritis meeting ACR/EULAR 2010 classification criteria and any one of the following:
  - a. Patient does not want to be on rheumatologic medications.
  - b. Patient has contraindications to standard rheumatologic medications.
  - c. Patient has failed treatment or an incomplete response with standard rheumatologic medications.
4. Women of childbearing age must have a negative pregnancy test and currently be on a reliable form of birth control.

**Exclusion Criteria:**

1. Severe depression
2. Dementia, mental disability
3. Claustrophobia
4. Uncontrolled seizure disorder
5. Uncontrolled asthma/severe COPD with  $pCO_2 > 45$  mmHg on arterial blood gas
6. Grade 4 congestive heart failure
7. Unstable angina
8. Chronic/acute otitis media/sinusitis
9. Major tympanic membrane trauma
10. Severe kyphoscoliosis
11. Prior chemotherapy with Bleomycin and evidence of deterioration in diffusion capacity of the lung for carbon monoxide (DLCO) after a single hyperbaric oxygen exposure.

**For Protocol Office use only:**

Protocol title: The Effects of Hyperbaric Oxygen on  
Rheumatoid Arthritis: a Pilot Study.  
FDG20160004H wAMD13

investigator name redacted 28 Jan 20

DGMC Human Research Protocol Template

12. History of renal insufficiency or GFR < 30
13. Women that are currently pregnant or breast feeding or intend on becoming pregnant while enrolled in the study

**Recruitment:**

1. Current or prior patients of the Rheumatology Clinic will be recruited by Rheumatology Clinic which is located in the Internal Medicine Clinic.
2. IRB-approved HIPAA waiver to contact patients that have been seen in the military treatment facility (MTF) within the past year with a diagnosis of rheumatoid arthritis
3. Flyers in the Rheumatology Clinic patient rooms.
4. Investigators may make an announcement at commander's calls after appropriate approvals have been made.

**Consent:**

Adequate study staff time will be set aside for each participant to receive information, ask questions and consider participation in the study. The consent process will begin with the introduction of the study. The Principal Investigator or study staff that have been delegated responsibility and have been trained on the protocol and consenting process, will explain the nature and scope of the study, potential risks and benefits of participation in lay terms and answer any questions the subject may have. At this point the subject will be asked to read the Informed Consent Document (ICD) and Health Insurance Portability and Accountability Act (HIPAA) authorization. If the subject has any further questions, they will be answered. When the subject has had all his/her questions answered, he/she will be offered the opportunity to participate in the study. If the participant has further questions, and wants to talk to a physician, one of the physicians on the study will be available to meet the prospective subject and answer any questions. This information will be discussed in a private area of the hospital or doctor's office.

The subject may elect to discuss the study with others if they so choose, prior to agreeing to participate. If the subject agrees to participate, the IRB approved ICD and HIPAA consent must be signed and personally dated by the subject and Investigator or study staff who have been delegated the responsibility and have been trained on the protocol before any study related procedures are done.

The original signed consent form will be turned into the protocol office and a copy will be placed in the subject's study folder and stored with other protected health information in a locked filing cabinet in an office that is locked when the office owner is not in the room. A copy of the ICD will be placed into their electronic medical record as well. Subjects will be assured that they may withdraw from the study at any time and for any reason and their medical treatment will not be compromised. Research procedures will not start until the IRB approved informed consent document has been signed and dated by the subject and research team member who has been delegated responsibility for consenting subjects and has been trained on the protocol.

**For Protocol Office use only:**

Protocol title: The Effects of Hyperbaric Oxygen on  
Rheumatoid Arthritis: a Pilot Study.  
FDG20160004H wAMD13

investigator name redacted 28 Jan 20

DGMC Human Research Protocol Template

**6.7. Safeguards for Protecting Subjects:**

The Medical Monitor as per 32 CFR 219.109 (e) and IAW DODI3216.02\_AFI 40-402 will serve as the subject advocate and ombudsman. He will have the right to discuss research progress with the principal investigator and staff. He will coordinate and review adverse event reports with the principal investigator. He may interview and consult on individual cases and reports to the IRB/PI any discrepancies or problems. The Medical Monitor may stop the research study in progress, remove individual subjects from a study, or take whatever steps are necessary to protect the safety and wellbeing of research subjects. The Medical Monitor will have the right and duty to review the study progress at varying intervals.

This study involves greater than minimal risk to subjects with the possibility of adverse subject reaction to the therapy. Primary monitoring of the study will be performed by the study team members, who will review accrual, adverse events (AEs), and treatment on a real-time basis. They will ensure that all eligibility criteria and consent requirements are met prior to a subject's participation in the study and that all study procedures and adverse event reporting occur according to the IRB approved protocol. They will follow all study participants, while on study treatment, on a real-time basis for development of adverse events and study endpoints, utilizing scheduled and as needed physical examinations and laboratory studies. Potential adverse events for this study are specifically listed in section 6.5.

Any event will be graded by severity and outcome. Study staff will make certain that all adverse events are recorded and reported according to DODI3216.02\_AFI 40-402 and SGSE Operating Instruction 40-402-01. Cumulative adverse events and study toxicities will be reviewed weekly. The study team will make decisions regarding treatment, cessation of accrual, and whether or not to close the study on the basis of frequency or severity of UPRISOs, Serious Adverse Events (SAEs). Any deviation, cessation in accrual or early study close will be communicated to the IRB immediately.

All SAEs, not related to progression of underlying disease, will be reported to the IRB immediately and when appropriate, the participant will be dis-enrolled from the study. All Unanticipated Problems Involving Risks to Subjects or Others (UPIRSOs) related or possibly related to the study will be reported by the PI/designee to the IRB according to SGSE Operating Instruction 40-402-01.

All study staff members will be informed by direct personal communication about any UPIRSOs or SAEs. If any protocol changes are needed, the PI will submit a modification request to the IRB. Protocol changes will not be implemented prior to IRB approval unless necessary to eliminate apparent immediate hazards to the research subjects. In such a case, the IRB will be promptly informed of the change following implementation (within 5 working days).

Serious adverse events can occur inside the hyperbaric chamber that can be either related, or unrelated to the exposure. Whenever an adverse event occurs, a stand-by hyperbaric staff

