**4. Purpose of Investigation**

This is a pilot study. The purpose of this investigation is to determine the effects and feasibility of using hyperbaric oxygen therapy (HBO2) for the treatment of rheumatoid arthritis joint pain and prevention of disease progression. In this study it is our intention to not only evaluate effects and feasibility but time, cost, adverse events and effect size in an attempt to predict an appropriate sample size and improve on the study design prior to a more extensive study.

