**Study Visits**

	Screening Visit (maybe split into 2 visits) ***	Base line Visit ***	HBO TX ***	Pain relief during HBOT	Compl etion of HBOT	Mo 3 (+/- 2 weeks)	Mo 6 (+/- 2 weeks)
--	--	--	---------------------------	--	------------------------------------	-----------------------------------	-----------------------------------

ICD/ HIPAA	X						
Inclusion/ Exclusion Criteria	X						
Exam by Hyperbaric Physician	X						
Trial HBOT	X						
Hyperbaric treatments			X 30 * **				
Rheumatology Visit		X		X		X	X
Labs		X		X	X	X	X
Ultrasound		X				X	X
MRI		X				X	X
DAS 28		X		X		X	X
RAPID 3		X	X ****	X		X	X
PSQ 3		X	X ****	X		X	X
VAS Pain		X	X *****	X		X	X

\*When subject reports pain relief during HBOT they will be assessed by Rheumatologist.

\*\* Complete 30 HBO treatments within 10 weeks.

\*\*\* Screening, Baseline, First HBOT treatment all within one month (four weeks)

\*\*\*\* at least 6 times while undergoing hyperbaric treatments

The optimal dose response of RA patients to HBO2 is unknown. Modest benefit has been shown in prior studies at 2 ATA and 1.5 bar for 10 and 9-11 sessions, respectively. The subject will be compressed with air in the hyperbaric chamber to 2.0 ATA, and then placed on 100% oxygen by a head tent or mask, for 90 minutes. After hood removal, the chamber is decompressed while the patient breathes chamber air. Treatments are daily, Monday through Friday for a planned total of 30 sessions. Time to change in subjective study outcomes (relief of joint pain, stiffness, improvement in sleep patterns, and increase in activity level) will be documented. Treatments will stop at the end of 30 sessions whether or not there is subjective improvement. After the initial assessment, follow-up with the rheumatologist is scheduled at three and six months which is standard of care for rheumatology patients. If the participant

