**For Protocol Office use only:**

Protocol title: The Effects of Hyperbaric Oxygen on  
Rheumatoid Arthritis: a Pilot Study.  
FDG20160004H wAMD13

investigator name redacted 28 Jan 20

DGMC Human Research Protocol Template

receiving hyperbaric therapy. Diabetics with blood sugar below this level receive juice and crackers, and may have blood glucose rechecked prior to therapy. Hyperbaric staff are always present in the hyperbaric chamber, and can monitor for signs or symptoms of hypoglycemia. At least one member of the hyperbaric team is present in the chamber for each eight patients in the chamber. If symptoms occur, staff will recheck the blood glucose immediately, and administer juice and crackers if needed. Following the completion of hyperbaric therapy, diabetic patients are again tested for blood sugar level. Patients must have a blood sugar level of at least 100 prior to leaving the hyperbaric medicine department, or be cleared by the hyperbaric physician.

**Fire** is always a risk with pressurized oxygen in high concentrations. Hyperbaric chamber patients are not allowed to smoke or carry lighters or flammable materials in the hyperbaric chamber. Until a recent explosion in a non-certified chamber, there had not been a fire in a United States hyperbaric chamber since 1968.

There is an **inconvenience of the time** associated with the study. There are approximately 40 appointments over a six month period. Thirty of them are two hour appointments for hyperbaric treatments.

**Blood draws:** there is a risk associated with blood draws. The risks of taking blood include: Pain, bruise at the point where the blood is taken, redness and swelling of the vein, infection and a rare risk of fainting.

**Ultrasound:** There is no risk associated with ultrasound.

**MRI:** We will be doing a MRI with and without contrast looking at the wrist from the distal radius to the mid diaphysis of the proximal phalanges. Risks include allergy to MRI contrast which is extremely rare. There is a risk of nephrogenic systemic fibrosis with poor renal function (GFR<30) that is screened for (see Attach 11) if the subject is over 50 years of age or has a history of renal insufficiency.

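### Active follow-up for adverse events is tied to the 6 to 10 treatment weeks, so how events are found in the 16 to 20 weeks afterwards is undefined

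*Combined protocol and SAP*

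**What the plan says.** Section 4 lists adverse events among the aims of the pilot, which is to "evaluate effects and feasibility but time, cost, adverse events and effect size".

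Section 6.7 then says of the study team: "They will follow all study participants, while on study treatment, on a real-time basis for development of adverse events and study endpoints". The sentence goes on to name the means, which are examinations (planned or as needed) and laboratory tests. It is the only sentence in the protocol that says participants are followed in order to find adverse events.

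Other duties in 6.7 carry no time limit: "Any event will be graded by severity and outcome"; "Study staff will make certain that all adverse events are recorded and reported according to" the cited outside instructions; and "Cumulative adverse events and study toxicities will be reviewed weekly". Serious events not related to progression of the disease go to the IRB immediately, and "when appropriate, the participant will be dis-enrolled from the study". The Incidental Findings part of 6.7 provides a shortened history and examination at each visit after the first.

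Section 6.4 sets the calendar. Treatment is given on weekdays, and a Study Visits footnote reads "Complete 30 HBO treatments within 10 weeks". Rheumatology visits follow at months 3 and 6, each with MRI, ultrasound, laboratory tests, DAS28 and questionnaires. Neither the text for these visits nor the table lists an adverse-event enquiry.

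**The concern.** The active search for events is worded to stop when treatment stops, and nothing in the later visit lists takes it up again. Three kinds of safety information are exposed:

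- **Effects that appear or persist after the course of sessions.** Section 6.5 describes progressive myopia that nearly always reverses, except where cataracts already exist. Whether it reversed is the outcome that 6.7 asks to be graded, and much of that answer would come after the last session.
- **Reactions to the later MRIs.** Section 6.5 says of the scan: "Risks include allergy to MRI contrast which is extremely rare". It also names nephrogenic systemic fibrosis when renal function is poor. The scans are research-driven (6.8), so their harms belong to the study.
- **The course of serious events in people who leave.** Dis-enrolment after a serious event is allowed, and the plan does not say whether safety follow-up continues.

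A pilot meant to inform a larger study would then carry forward adverse-event rates whose observation period is unclear.

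**Working it through.** The plan states no adverse-event window, so there is no figure to reproduce. The check is calendar arithmetic followed by a comparison of sections.

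**Inputs**

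- 30 sessions, Monday to Friday (6.4, text after the Study Visits table).
- At most 10 weeks to complete them (6.4, item 6, and the table footnote).
- Baseline is the date of the first session (6.4, item 4).
- Month 3 and month 6 visits are counted from baseline, each +/- 2 weeks (6.4, items 8 and 9; item 8 omits the unit, which the table gives as weeks).
- MRI at baseline, month 3 and month 6 (6.3, item 5; Study Visits table; 6.8 counts three).

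**Time after treatment**

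1. Shortest treatment period: 30 / 5 = 6 weeks. Longest: 10 weeks.
2. Six months: 6 x 365.25 / 12 / 7 = 26.1 weeks, taken as 26.
3. Weeks after treatment: 26 - 10 = 16 (16/26 = 62%) to 26 - 6 = 20 (20/26 = 77%).
4. With the month 6 window: 24 - 10 = 14 to 28 - 6 = 22 weeks.

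The count starts at the first session. The trial hyperbaric session falls in the screening period, up to four weeks earlier, and is not in these figures.

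**Position of the later MRIs**

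Month 3 is 13.0 weeks from baseline, so the earliest visit is 13 - 2 = week 11, one week after the latest end of treatment. The month 6 scan is clearly later. The month 3 scan is ordered ahead of its visit with no earliest date, so a late finisher's scan could overlap the last treatment week. Two of three MRIs therefore normally fall after treatment.

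Contrast is stated for baseline in 6.4 and for the MRI in general in 6.5. Three metabolic panels per participant (6.8), with the panel drawn before MRI (6.4), fit three contrast scans. That is an inference.

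**What operates after the last session**

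| Provision | Limited to treatment? | Does it elicit events? |
|---|---|---|
| Real-time follow-up of participants (6.7) | Yes | Yes |
| Recording, grading, weekly review (6.7) | No | No; acts on events already known |
| Serious-event reporting (6.7) | No | No; acts on events already known |
| Plan for worsening RA symptoms (6.4) | No | Only through worsening RA |
| Daily monitoring by hyperbaric physicians (6.4) | Yes | Yes |
| History and examination at later visits (6.7, Incidental Findings) | No | Possibly; not described as adverse-event collection |
| Month 3 and month 6 visit lists (6.4) | No | No adverse-event item |

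**Illustration of open events**

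Section 6.5 gives 20% to 69% for visual change in prolonged courses. If that range applied to 30 sessions, which the protocol does not claim, then among 10 participants with complete data 0.20 x 10 = 2 to 0.69 x 10 = 6.9, or about 2 to 7, could finish treatment with a change whose outcome is still to be recorded.

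**The case against.** The strongest reply is that the sentence sets how intensively participants are watched during treatment and does not end collection. It does not say only. Its neighbours require all events to be recorded and any event to be graded, with no end date, and serious events remain reportable. The same sentence also mentions study endpoints, which are plainly measured at months 3 and 6. If the treatment limit does not shut off endpoints, it should not be read as shutting off adverse events. Later visits include a history and examination. The missing table row proves little, because the table has no such row for the treatment sessions either, where monitoring is clearly provided. The outside instructions cited in 6.7 may define a window, and they are not part of these documents.

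Most of this stands. A reader might infer that the plan follows adverse events on treatment only and leaves out everything later. The documents do not support that, because the recording and reporting duties have no time limit. Nor do they show that the pilot would report a falsely favourable safety profile. Section 6.5 calls contrast allergy extremely rare, renal insufficiency or GFR below 30 is an exclusion (6.6), and at most 20 subjects are recruited, so few events from the later scans would be expected. Dis-enrolment is discretionary, and the text does not say that safety follow-up then ends.

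What the reply does not supply is a step that finds events after treatment. Recording and grading need an event to be known first. The later history and examination is described under Incidental Findings, which concerns unrelated conditions, and the month 3 and month 6 lists are itemised without an adverse-event enquiry.

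**Conclusion.** The point holds in this form: active follow-up for adverse events is stated for the treatment period, and for the next 16 to 20 of about 26 weeks (14 to 22 with the visit window) the protocol defines no step that elicits events or records whether earlier ones resolved. Events in that time are recordable and, if serious and not due to disease progression, reportable, but their discovery is left to unprompted reporting or to a visit not described for that purpose. Because adverse events are a stated aim, this should be changed.

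Under-ascertainment is possible, and its size is unknown. It would be tempting to read 62% to 77% as the share of events lost. It is a share of calendar time, and the documents give no event rate by period from which a loss could be computed.

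The conclusion assumes that being on study treatment means the course of 30 sessions, that this course takes 6 to 10 weeks, and that the outside instructions do not already set a collection window. If they do, the remaining work is to state that window in the protocol and reconcile 6.7 with it.

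**What to change.** - In 6.7, replace the treatment limit in the follow-up sentence with a period running from the trial hyperbaric session through the month 6 visit. This also removes the conflict with endpoints measured at months 3 and 6.
- In the Study Visits table (6.4), add an adverse-event row covering the trial session, each treatment session, completion of treatment, month 3 and month 6.
- State that events still open at completion are followed to resolution or month 6, whichever comes first.
- In 6.7, state that a subject dis-enrolled after a serious event stays in safety follow-up to month 6 unless consent is withdrawn. This concerns data collection and changes no rule on stopping treatment.

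The cost is protocol wording and one table row, since the month 3 and month 6 visits already exist. The downside is a few more recorded events and a slightly higher reported event rate.

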**For Protocol Office use only:**

Protocol title: The Effects of Hyperbaric Oxygen on  
Rheumatoid Arthritis: a Pilot Study.  
FDG20160004H wAMD13

investigator name redacted 28 Jan 20

DGMC Human Research Protocol Template

member will immediately be compressed in one of the connected chambers, enter the main treatment chamber, and accompany the patient to the transport chamber to be decompressed to the surface for definitive medical care. If necessary, an appropriate code can be called, or the patient may be immediately transported to the emergency room for further management.

Standard measures for protection of subject privacy and confidentiality that are currently being practiced will continue. All electronic data will be housed on a Common Access Card enabled computer accessible only to study personnel within a secured office. All access to the subject computer will be logged. All electronic transmissions of data will be encrypted over a secured network. All electronic data and hard copy records obtained as a result of the HIPAA waiver, will be deleted or shredded after contact has been made or no contact has been successful. All hard copy records will be stored in a locked hyperbaric medicine file cabinet in a secure room for the duration of the study. Upon the close of the study all records will be transferred to the CIF for storage for three years then staged to storage according to IAW DODI 3216.02\_AFI40-402 and USAF policies.

**Incidental Findings**

All study participants will receive a complete history and physical examination by a Rheumatologist at the start of the study and abbreviated history and physical examinations at each visit thereafter. Each participant will have a history and physical examination by a hyperbaric physician to determine appropriateness for hyperbaric oxygen exposures. During these assessments, patients occasionally complain of symptoms unrelated to the study purpose. During the physical examinations, it is possible that a secondary condition will be detected. When unrelated medical conditions are detected or suspected by the hyperbaric physicians, the subject will be referred to their provider and may be referred to an appropriate physician for further evaluation. A report of all incidental findings will be entered into a written report that will be placed in the subject's electronic medical record

Previously undiagnosed medical conditions that are discovered unintentionally and are unrelated to the current subject of research will, when actionable, be reported to the IRB in a timely manner based upon the suspected condition or disease severity. In coordination with the IRB, and a qualified specialist the PI will verify the finding. Depending upon the severity of the condition or disease the subject or subjects legal representative will be contacted by the PI via phone or letter or an in person communication.

**Data Entry:** Data will be entered by authorized study personnel only. Upon completion of data entry all hard copy documents will be stored as per the hard copy records policy outlined below. All electronic Protected Health Information (PHI) data will be housed on the DGMC EPHI drive and will only be accessible via a Common Access Card enabled computer accessible only to study personnel within a secured office. All electronic transmissions of data will be encrypted over a secured network.

**Data security and transfer:** Study documents will reside in the Clinical Investigation Facility within the 60MDG SGSE Directory in a limited access password protected directory designated

